# 1 PROTOCOL SYNOPSIS

Financial Disclosure for US FDA Submission Required?	Yes X No
Test Article(s) / Product(s):	Centurion® Vision System – version 2.04 45° Balanced Tip*
Objective(s):	*Used with INTREPID® Ultra Sleeve Primary objective is to demonstrate that the Centurion® Vision System used with the 45° Balanced Tip will result in less Cumulative Dissipated Energy (CDE) than the Infiniti® Vision System used with the 45° Mini-Flared Kelman (MFK) tip during cataract extraction surgery via phacoemulsification of cataract grades NII- NIV (LOCSII).  The Secondary objectives for this study are as follows;  1. Demonstrate that the Centurion® Vision System used with the 45° Balanced Tip will result in less CDE than the Centurion® Vision System used with the 45° MFK tip during cataract extraction surgery via phacoemulsification of cataract grades NII-NIV (LOCSII).  2. Demonstrate that the Centurion® Vision System used with the 45° Balanced Tip will result in less BSS Fluid Used than the Infiniti® Vision System used with the 45° MFK tip during cataract extraction surgery via phacoemulsification of cataract grades NII-NIV (LOCSII).  3. Demonstrate that the Centurion® Vision System used with the 45° MFK tip will result in less BSS Fluid Used than the Infiniti® Vision System used with the 45° MFK tip during cataract extraction surgery via phacoemulsification of cataract grades NII-NIV (LOCSII).  4. Demonstrate that the Centurion® Vision System used with the 45° MFK tip will result in less CDE than the Infiniti® Vision System used with the 45° MFK tip during cataract extraction surgery via phacoemulsification of cataract grades NII-NIV (LOCSII).

Document: TDOC-0050176 Version: 2.0; Effective; CURRENT

Status: Effective Page 3 of 75

Document: TDOC-0050176 Version: 2.0; Effective; CURRENT

Status: Effective Page 4 of 75

Effective Date: 18-Jul-2016

Clinical Trial Design:	Prospective, parallel, randomized, patient-masked, 3-arm, multi-	
	center clinical study following subjects with surgery done with:	
	
 
Centurion® Vision System, 45°Balanced Tip1
 
Centurion® Vision System, 45°Mini Flared Kelman Tip1
 
Infiniti® Vision System, 45°Mini Flared Kelman Tip2
 
	
	1Used with INTREPID® Ultra Infusion Sleeve	
	2 Used with Ultra infusion Sleeve	
	Phaco-emulsification of a harder lens requires more CDE and more BSS fluid. For this study, the softest lenses (LOCSII Opacities N0 and NI) will be excluded, leaving all lenses with LOCSII Opacities NII-NIV.	
	For each group, cataract surgery will be performed on subjects who will be randomized with an equal number having their surgery performed with each configuration.	
	Clear Cornea Incision: 2.2mm-2.4mm	
	Approximately 177 subjects (59 per group) randomized with an	
No. of Subjects:	expectation to have at least 159 completed subjects (53 per group) for evaluability.	
Region(s):	Approximately 5 investigational sites across the USA, LACAN, Asia-Pacific and EMEA	
Clinical Trial	a) Total expected duration of clinical investigation: approximately	
Duration:	12 months	
	b) Expected duration of each subject participation: up to 5 months c) Planned follow-up duration for each subject: up to 3 months	
	postoperative	
	d) Estimated subject recruitment period (time needed to select the number of patients): approximately 6 months	

Document: TDOC-0050176 Version: 2.0; Effective; CURRENT

Status: Effective Page 5 of 75

Clinical Trial Population:	Adult subjects of 21 years of age and above requiring cataract extraction followed by IOL implantation. Nuclear Opalescence II to IV using LOCS II.	
Treatments:	Test Article:	Centurion ® Vision System - version 2.04 45°Balanced Tip   Used with INTREPID ® Ultra Infusion Sleeve
	Administration:	Surgical instrumentation
	General Description:	Centurion ® Vision System (v2.04) will be used with the 45° Balanced Tip (coupled with the INTREPID ® Ultra Infusion sleeve) for phaco-emulsification procedure.
	Duration of Treatment:	One time routine surgical procedure followed by 3 months (+/- 14 days) of postoperative follow-up.
	Control Article:	Centurion ® Vision System (version 2.04) with 45° Mini Flared Kelman u/s Tip  (with INTREPID ® Ultra infusion sleeve)  Infiniti ® Vision System (version 3.01) with
		45° Mini Flared Kelman u/s Tip   Used with INTREPID ® Ultra Infusion Sleeve  Used with Ultra infusion Sleeve
	Administration:	Surgical instrumentation
	General Description:	Centurion® Vision System (version 2.04) will be used with the 45° Mini Flared u/s Tip coupled with INTREPID® Ultra infusion sleeve) for phaco-emulsification procedure.
		Infiniti ® Vision System (version 3.01) will be used with 45° Mini Flared Kelman u/s Tip (coupled with Ultra Infusion Sleeve) for phaco-emulsification procedure.
	Duration of Treatment:	One time routine surgical procedure followed by 3 months (+/- 14 days) of postoperative follow-up.
Inclusion & Exclusion Criteria:	Detailed information on inclusion and exclusion criteria can be found in Section 10:Subject Population	

### **Assessments**:

Primary Variable	- Cumulative Dissipated Energy (CDE)

Document: TDOC-0050176 Version: 2.0; Effective; CURRENT

Status: Effective Page 6 of 75

[ ~		
Secondary	- CDE (depending on the objective)	
Variables	Balanced Salt Solution (BSS) fluid used	
	- Adverse Events (including SSIs)	
	- Slit-lamp examination	
	- Anterior chamber cells	
	- Anterior chamber flare	
	- Corneal oedema	
Safety	- Endothelial cell count	
Variables	- Dilated fundus examination	
	- BCDVA	
	- IOP	
	- Problems during surgery	
	- IOL placement	
	- Device deficiencies	

Document: TDOC-0050176 Version: 2.0; Effective; CURRENT

Status: Effective Page 7 of 75

#### **Statistical Analysis:**

- **Safety Data Set**- Safety analyses will be conducted using the safety analysis set on a treatment- emergent basis. The Safety data set will include all subjects/ eyes exposed to any study procedures evaluated in this study.

- Intent-to-Treat (ITT) Data Set will include all subjects who are randomized in the study and receive treatment. The ITT set will be the primary analysis set for efficacy.
- **Per Protocol Set (PPS)** The PP set is a subset of ITT which excludes those who meet the critical deviation criteria as specified in the Deviations and Evaluability Plan. Supportive analyses of the primary and secondary endpoints will be conducted using the PP set if the number of subjects excluded from PP exceeds 5% of the ITT.

Safety summaries will be reported by treatment. For safety variables, all variables will be summarized descriptively by treatment group. No inferential testing will be performed for safety. If more than 5% of subjects are excluded due to deviations, the PPS will become the primary analysis set, and will be compared to the ITT to check for robustness of the results.

A sequential (closed) testing procedure will be used to control type I error rate due to multiplicity for primary and secondary endpoints at one- sided 0.05 significant level.

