### 7.2 Clinical Trial Design

Prospective, parallel, randomized, patient-masked, 3-arm, multi-center clinical study following subjects with surgery done with:

- Centurion® Vision System, 45°Balanced Tip
- Centurion® Vision System, 45°Mini Flared Kelman Tip¹
- Infiniti® Vision System, 45°Mini Flared Kelman Tip

Phaco-emulsification of a harder lens requires more CDE and more BSS fluid for this study, the softest lenses (LOCSII Opacities NO and N1) will be excluded, leaving all lenses with LOCSII Opacities NII-NIV.

The clear cornea incision will be between 2.2mm and 2.4mm.

A randomization list will be generated by Sponsor personnel who is not involved in the day-to-day conduct of the study, and who does not have contact with the study subjects, the site, or the Alcon employees who do have site contact.

Print Date:

<sup>1Used with INTREPID® Ultra Infusion Sleeve

<sup>2Used with Ultra infusion Sleeve

**Document:** TDOC-0050176 **Version:** 2.0; Effective; CURRENT

[figure not shown]
Status: Effective Page 22 of 75

Randomized treatment assignment will be provided via Interactive Randomization Technology (IRT).

This is a subject-masked study and not observer-masked. Subjects will be masked to the treatment for the study eye. The surgeon (Investigator) is not masked to treatment as this is an impossibility with the medical devices studied here. Site personnel not participating in surgery and not requiring knowledge of randomization will be masked to the extent possible. Investigative sites will take all precautions necessary to ensure the subjects remain masked for the duration of the trial. It is encouraged that the Investigator take the opportunity to remind the subject that he/she will be masked for the duration of the trial.

Post-operatively (day 0), the subject will be required to attend follow-up visits at day 1, day 7 (+/- 2 days) and month 3 (+/- 14 days).

Figure 7–1 Study Design

Document: TDOC-0050176 Version: 2.0; Effective; CURRENT

Status: Effective Page 23 of 75

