#### 15 ANALYSIS PLAN

## 15.1 Subject Evaluability

The final subject evaluability will be determined prior to locking the database.

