## 15.2.2 Intention-to-Treat (ITT) Analysis Set

The ITT set will include all subjects will include all subjects who are randomized in the study and receive treatment. The ITT set will be the primary analysis set for efficacy.

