## 15.2.3 Per-Protocol (PP) Analysis Set

The PP set is a subset of ITT which excludes those who meet the critical deviation criteria as specified in the Deviations and Evaluability Plan. Supportive analysis of the primary and secondary endpoints will be conducted using the PP set if the number of subjects excluded from PP exceeds 5% of the ITT.

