2.1 Performance Analysis Sets

The ITT set will include all subjects who are randomized in the study and receive procedure. The ITT set will be the primary analysis set for performance.

The PPS is a subset of ITT which excludes those who meet the critical deviation criteria as specified in the Deviations and Evaluability Plan. Supportive analysis of the primary and secondary endpoints will be conducted using PPS if the number of subjects excluded from PPS exceeds 5% of the ITT.

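### Above 5% deviation exclusions, one synopsis sentence makes the per-protocol set primary while every other statement keeps ITT primary

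*Protocol*

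**What the plan says.** Two rules for the primary analysis set stand in the current text.

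- **Fixed rule.** Protocol 15.2.2 states "The ITT set will be the primary analysis set for efficacy", and SAP 2.1 states "The ITT set will be the primary analysis set for performance". Neither attaches a condition. Protocol 15.2.3 gives the per-protocol (PP) set its role: "Supportive analysis of the primary and secondary endpoints will be conducted using the PP set", if exclusions from PP exceed 5% of the ITT. SAP 2.1 repeats this. The synopsis section on statistical analysis also states this rule, with the same 5% limit, in its definitions of the sets: "Supportive analyses of the primary and secondary endpoints will be conducted using the PP set if the number of subjects excluded from PP" is above that limit.
- **Switching rule.** Later in that synopsis section: "If more than 5% of subjects are excluded due to deviations, the PPS will become the primary analysis set". The sentence goes on to say that the PPS will be compared with ITT as a check of robustness.

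The exclusions are critical deviations listed in a separate Deviations and Evaluability Plan. On timing, protocol 15.1 says "The final subject evaluability will be determined prior to locking the database". On masking, protocol 7.2 says "The surgeon (Investigator) is not masked to treatment as this is an impossibility with the medical devices studied here". CDE is read from the console at the end of surgery (protocol 12.1.2.6.1).

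**The concern.** Exceeding 5% PP exclusions leads to two different primary analyses, and neither document ranks synopsis, body and SAP. Two analysts could each follow the protocol, report different primary results and cite a sentence in support.

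The two rules also differ in quality. The fixed rule names one set in advance. The switching rule lets the number of exclusions choose the set, and it chooses the one formed after randomisation. By the time evaluability is settled, CDE has been recorded and the surgeon knows the treatment. Protocol 15.1 requires the decision before database lock but does not say that it is made without sight of treatment or CDE. For a one-sided superiority test, moving the primary comparison away from the groups as randomised and treated needs a justification, and none is given.

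**Working it through.** **Inputs.** Difference −7.4, SD 15.2, one-sided 0.05, 80% power, 53 per group, 10% dropout, 59 per group and 177 in total (protocol 15.10, SAP 6). Trigger: more than 5% (synopsis, protocol 15.2.3, SAP 2.1). The documents give no rate of critical deviations, so the rates below are assumptions.

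**1. The plan's own figure.** n = 2 × 15.2² × (1.645 + 0.842)² / 7.4² = 52.2, so 53 per group. The exact t-test power at 53 is 80.1%. Then 53 / 0.9 = 58.9, so 59, and 3 × 59 = 177. The stated sample size reproduces.

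**2. The trigger as a count.** 5% × 177 = 8.85, so 9 exclusions. If the ITT set were as small as 159, 5% × 159 = 7.95, so 8.

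**3. Chance of reaching it.** P(Binomial(177, p) ≥ 9):

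| Assumed critical-deviation rate | P(9 or more of 177) |
|---|---|
| 2% | 0.010 |
| 3% | 0.087 |
| 5% | 0.527 |
| 10% | 0.994 |

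The planned 10% dropout is not this rate. CDE is recorded at surgery, so later loss to follow-up does not remove it.

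**4. How far the two sets can disagree.** Simulation of a one-sided two-sample t-test (not the planned ANCOVA), 59 per arm, random exclusion of 3 or 6 subjects in each compared arm (9 or 18 of 177 over three arms), 200,000 runs each:

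| Quantity | 3 per arm | 6 per arm |
|---|---|---|
| Error if success may be claimed on either set | 0.0597 | 0.0635 |
| Opposite verdicts, no true difference | 0.0189 | 0.0263 |
| Opposite verdicts, difference −7.4 | 0.0478 | 0.0745 |
| Power on PPS (ITT about 84%) | 82.0% | 80.0% |

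A normal approximation agrees. The two test statistics correlate at √(56/59) = 0.974 or √(53/59) = 0.948. The either-set error is 0.05 + 0.05 − P(both reject), which gives 0.059 and 0.063.

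**5. Allowing for the chance that the trigger is not reached.** Either-set error ≈ 5% + P(trigger) × excess, with the excess 0.97 or 1.35 percentage points from step 4. At a 3% rate: 5 + 0.087 × 0.97 to 1.35 = 5.1%. At 5%: 5 + 0.527 × 0.97 to 1.35 = 5.5% to 5.7%. At 10%: 5 + 0.994 × 0.97 to 1.35 = 6.0% to 6.3%.

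**6. Exclusions related to CDE.** With equal numbers excluded in both compared arms (60,000 runs), the PPS test alone has this error:

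| Correlation of exclusion with CDE | 3 per arm | 6 per arm |
|---|---|---|
| 0.3 | 0.052 | 0.051 |
| 0.5 | 0.054 | 0.055 |
| 1.0 | 0.065 | 0.075 |

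Larger inflation would need CDE-related exclusions concentrated in one arm. Nothing in the documents shows that this would happen.

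**The case against.** The strongest reply is that this is a drafting leftover. The switch appears once. The dedicated analysis sections of both documents agree on ITT, as do the synopsis's own definitions, and the SAP's success criterion mentions no switch. By ordinary convention the SAP would govern. That is a sensible guess at intent, but neither document states the convention, and the SAP does not record departing from the synopsis.

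A second reply is that the error figures assume a freedom that no sentence grants. This is correct. Each rule names one set, and under random exclusion either rule applied alone holds about 5%. The 6.0% to 6.4% describes what the ambiguity would allow, and only once the trigger is met. The opposite-verdict figures likewise reflect ordinary disagreement between a set and a slightly smaller subset. With 6 excluded per arm the PPS still has the planned 53.

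Three smaller points also stand. Settling evaluability before lock is a partial safeguard. The ITT set is itself limited to subjects who received treatment, so the contrast with PPS is one of degree. The triggers are worded differently: 8 exclusions would be 5.0% (just over the limit) of an ITT set of 159 but 4.5% of 177 randomised.

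Reading the sentence as being about safety, because it follows the safety lines, does not work. Safety has its own analysis set and no inferential testing, whereas ITT and PPS are defined for efficacy.

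**Conclusion.** The contradiction is real and should be removed before database lock. At or below 5% exclusions all texts agree on ITT; above it they do not, and the primary set is not uniquely specified. The case rests on that ambiguity, and on the synopsis rule being a data-dependent switch, more than on the size of the error. That size is modest: at most about 1.4 percentage points of extra one-sided error under random exclusion with a free choice of set, and a conflicting primary verdict in about 5% to 7% of trials at the planned effect. These figures assume 3 or 6 exclusions per arm and a t-test in place of the ANCOVA. How likely the trigger is cannot be judged without a critical-deviation rate. The statement that nothing ranks the two rules covers the protocol and SAP only; the Deviations and Evaluability Plan was not available.

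**What to change.** Delete the switch sentence from the synopsis. The synopsis then agrees with its own definitions, with protocol 15.2.2–15.2.3 and with SAP 2.1: ITT is primary whatever the number excluded, and PP is supportive. The 5% condition for running the PP analysis can stay. The cost is a one-sentence edit to the synopsis. Sample size, data collection, protocol 15.2 and SAP 2.1 need no change.

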### **Primary:**

The primary hypothesis is to demonstrate that the Centurion® Vision System used with the 45° Balanced Tip will result in less Cumulative Dissipated Energy (CDE) than the Infiniti® Vision System used with the 45° Mini Flared tip during cataract extraction surgery via phacoemulsification:

 $H_o$ :  $\mu_{centurion \ Bal \ CDE} \ge \mu_{lnfiniti \ MFK \ CDE}$ 

 $H_A$ :  $\mu_{centurion Bal CDE} < \mu_{Infiniti MFK CDE}$ 

 $\mu_{centurion\_Bal\ CDE}$  and  $\mu_{Infiniti\_MFK\ CDE}$  are the true mean values of the primary performance endpoint, CDE under Centurion with the Balanced Tip, and Infiniti with the Mini Flared Kelman (MFK) tip, respectively.

The difference of CDE between two groups will be examined by using an analysis of covariance model (ANCOVA) adjusting for site and baseline opacity grade. Display of ANCOVA results in summary tables will contain difference between LS means, a one-sided p- value < 0.05 will conclude superiority of Centurion® over Infiniti® group.

#### Secondary:

The difference between two groups will be examined by using ANCOVA adjusting for site and baseline opacity grade. Display of ANCOVA results in summary tables will contain difference between LS Means, a one-sided p- value <0.05 will conclude superiority.

**Document:** TDOC-0050176 **Version:** 2.0; Effective; CURRENT

Status: Effective Page 8 of 75

#### **Safety:**

Demographics and baseline characteristics will be summarized overall and by treatment arm. Other exploratory and safety variables will be summarized descriptively. Continuous measurements will be presented using n, mean, standard deviation, minimum, maximum and confidence intervals at each visit. Categorical measurements will be tabulated with the number and percent in each category at each visit.

### **Sample Size Justification:**

Based on previous studies, a sample size of 53 in each group will have 80% power to detect a difference in means of -7.4 (the difference between a Group 1 mean,  $\mu_1$ , of 38.5 and a Group 2 mean,  $\mu_2$ , of 45.9) assuming that the common standard deviation is 15.2 using a two group t-test with a 0.05 one-sided significance level. Assuming a 10% dropout rate, approximately 59 subjects per group (177 in total) will be randomized.

Status: Effective Page 9 of 75

Effective Date: 18-Jul-2016

# **3 ABBREVIATIONS**

Abbreviation	Definition
ADE	Adverse Device Effect
AE	Adverse event
ASADE	Anticipated Serious Adverse Effect
Asp	Aspiration
BCDVA	Best Corrected Distance Visual Acuity
BSS	Balanced Salt Solution
CDE	Cumulative Dissipated Energy
CRF	Case report form
CV	Coefficient of Variance
CVS	Centurion® Vision System
CS	Clinically significant
DD	Device Deficiency
EC	Ethics Committee
ECD	Endothelial Cell Density
EMEA	Europe, Middle-east and Africa
ESCRS	European Society of Cataract and Refractive Surgeons
ETDRS	Early Treatment Diabetic Retinopathy Study
FDA	US Food and Drug Administration
GCP	Good Clinical Practice
HIPAA	Health Insurance Portability and Accountability Act
IB	Investigator brochure
IEC	Independent ethics committee
ICD	Informed Consent Documentation
ICH	International Conference on Harmonization
ITT	Intent-to-Treat
IRB	Institutional review board
IRT	Interactive randomization technology
IOL	Intraocular lens
IOP	Itnraocular Pressure
ISO	International Organization for Standardization
ITT	Intent-to-Treat
IVS	Infiniti® Vision System
JCRS	Journal of Cataract and Refractive Surgery
LACAN	Latin America and Canada
LASIK	Laser-Assisted in situ Keratomileusis
LOCSII	Lens opacities classification system II
LogMAR	Logarithm of the Minimum Angle of Resolution
LRI	Limbal Relaxing Incision
MOP	Manual of Procedure
MedDRA®	Medical Dictionary for Regulatory Activities

Document: TDOC-0050176 Version: 2.0; Effective; CURRENT

Status: Effective Page 15 of 75

Abbreviation	Definition		
MFK tip	Mini-Flared Kelman tip		
NSAID	Non-steroidal anti-inflammatory drug		
NCS	Not clinically significant		
PI	Principal Investigator		
PPS	Per-Protocol Set		
PP	Per protocol		
POD	Post-Operative Day		
POW	Post-Operative Week		
SAE	Serious adverse event		
SADE	Serious Adverse Device Effect		
SAS®	SAS statistical software, SAS Institute Inc., Cary, NC		
SSI	Secondary Surgical Intervention		
TDOC	Technical document (Alcon numbering system for internal documents)		
u/s	Ultra-sound		
μ	Mean		
UCDVA	Uncorrected Distance Visual Acuity		
USA	United States of America		

Document: TDOC-0050176 Version: 2.0; Effective; CURRENT

Status: Effective Page 16 of 75

Effective Date: 18-Jul-2016

# 4 GLOSSARY OF TERMS

Adverse Device Effect (ADE)	Adverse event related to the use of an investigational medical device or comparator, if applicable. Note: This definition includes adverse events resulting from insufficient or inadequate instructions for use, deployment, implantation, installation, or operation; any malfunction; and use error or intentional misuse of the investigational medical device or comparator, if applicable.
Adverse Event (AE)	Any untoward medical occurrence, unintended disease or injury, or untoward clinical signs (including abnormal laboratory findings) in subjects, users or other persons, whether or not related to the investigational medical device. Note: For subjects, this definition includes events related to the investigational medical device, the comparator, or the procedures involved. For users or other persons, this definition is restricted to events related to investigational medical devices.
Anticipated Serious Adverse Device Effect (ASADE)	Serious adverse device effect which by its nature, incidence, severity, or outcome has been identified in the risk analysis.
Assessment	A procedure used to generate data required by the study.
Device Deficiency	Inadequacy of a medical device with respect to its identity, quality, durability, reliability, safety, or performance. Note: This definition includes malfunctions, misuse or use errors, and inadequate labeling.
Performance (Clinical)	Behavior of a medical device or response of the subject to that medical device in relation to its intended use, when correctly applied to appropriate subjects.
Malfunction	Failure of an investigational medical device to perform in accordance with its intended purpose when used in accordance with the instructions for use or clinical investigation plan.
Nonserious Adverse Event	Adverse event that does not meet the criteria for a serious adverse event.
Period	A minor subdivision of the study timeline; divides phases into smaller functional segments such as screening, baseline, operative, postoperative, etc.
Randomization Number	A unique identifier assigned to each randomized subject, corresponding to a specific treatment arm assignment.
Serious Adverse Device Effect (SADE)	Adverse device effect that has resulted in any of the consequences characteristic of a serious adverse event.

Document: TDOC-0050176 Version: 2.0; Effective; CURRENT

Status: Effective Page 17 of 75

	_		
Serious Adverse	Adverse event that led to any of the following:		
Event (SAE)	Death.		
	A serious deterioration in health that either resulted in:		
	a) a life-threatening illness or injury.  Note: Life-threatening means that the individual was at immediate risk of death from the event as it occurred, ie, it does not include an event which hypothetically might have caused death had it occurred in a more severe form.		
	b) permanent impairment to a body structure or a body function.		
	c) in-patient hospitalization or prolonged hospitalization.  Note: Planned hospitalization for a pre-existing condition, or a procedure required by the clinical investigation plan, without serious deterioration in health, is not considered a serious adverse event. In general, hospitalization signifies that the individual remained at the hospital or emergency ward for observation and/or treatment (usually involving an overnight stay) that would not have been appropriate in the physician's office or an out-patient setting. Complications that occur during hospitalization are AEs. If a complication prolongs hospitalization or fulfills any other serious criteria, the event is serious. When in doubt as to whether "hospitalization" occurred, the event should be considered serious.		
	d) a medical or surgical intervention to prevent a) or b).		
	e) any indirect harm as a consequence of incorrect diagnostic test results when used within manufacturer's instructions for use.		
	Fetal distress, fetal death, or a congenital abnormality or birth defect.		
Subject Number	A number assigned to each subject who enrolls in the study. When combined with the site number, a unique identifier is created for each subject in the study.		
Unanticipated Serious Adverse Device Effect (USADE)	Serious adverse device effect which by its nature, incidence, severity or outcome has not been identified in the risk analysis.		

**Document:** TDOC-0050176 **Version:** 2.0; Effective; CURRENT

Status: Effective Page 18 of 75

